## C. Sample Size, Statistical Methods, and Power Calculation

### C1. Analytic and statistical methods (including randomization)

**Randomization.** Thirty-six primary care practices from the rural Midwestern U.S. will be randomly allocated in equal proportions (1:1:1) to each of the three arms (FFS, PCMH, DM). Randomization will be stratified by institutional affiliation (KUMC, UNMC, Marshfield Clinic) within three cohorts.

**Missing data.** Based on our prior history using a similar retention plan in the rural setting, we expect to retain a minimum of 80% of participants (with a goal of 90%) at 24 months across all three treatment arms. We will document reasons for loss to follow-up. Participants who are removed from study for pregnancy, bariatric surgery, medical safety reasons, behavioral problems, or death will be excluded from analyses. All primary analyses will be conducted using intent-to-treat. We will evaluate the missing data pattern for differential loss to follow-up based upon treatment arm. All of the covariates (other than the outcomes) will be collected at baseline, and with our data quality controls we don't expect this data to be missing. In the absence of differential loss to follow-up, missing weight data will be treated as missing at random and addressed using maximum likelihood methods.

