### **Primary aims 1-3: weight loss at 24 months and leading up to 24 months**

Weight loss at 24 months will be compared between PCMH vs FFS and DM vs FFS, as well as DM vs PCMH. Hierarchical linear mixed models will be used to examine the group differences, accounting for the correlation between patients from the same clinic.

We will fit a hierarchical linear mixed model with longitudinal weight change at 6, 18, and 24 months study visits. This model will account for the correlation between patients in the same clinic as well as correlation of measures from the same patient. In secondary analysis, percent weight loss will also be compared across the three groups using the same approach. Clinical cutpoints of 5% and 10% will be compared across arms at 6 and 24 months using generalized linear mixed models. The analytical plans may be adapted to provide the best approach using the latest methodological advancements.

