## **E2e. Outcome measures**

Outcome measures have been selected with input from our Patient Advisory Board and are supported by the literature. See Table 5 for the list of measures and estimated time to complete. The goal will be to complete the assessment visits within a -7 days/+21 day window of the target date. We will allow for a 3 month window for 6 and 18 month visits if an assessment visit appointment needs to be rescheduled and a 4 month window for the 24 month visit if an assessment visit appointment needs to be rescheduled. Chart review may be used to capture medications and number of clinic visits as well as missing weight data.

**Anthropomorphic measures.** Weight, and blood pressure will be directly measured and recorded at baseline, 6, 18, and 24 months during in-clinic assessment visits. Height will be measured at baseline only. These measures will be collected by clinic staff. Participants will be weighed in light clothing (shorts and t-shirt) in a fasting state using a calibrated digital scale accurate to 0.1 kg. Height will be measured with a stadiometer to calculate BMI. Blood pressure will be measured by clinic staff after the patient rests in a seated position for 5 minutes. Two measurements will be taken and recorded. If either the systolic or diastolic measurements are greater than 5mm Hg apart, a third measurement will be taken after a one-minute break. Estimated time for in-person assessment visit procedures is 15-20 minutes. If a patient is unable to come to the clinic for the data collection visit, an in-home visit or a visit at another location convenient for the patient, may be conducted.

**Fasting glucose and lipids.** A clinic phlebotomist or nurse will collect blood samples required for analysis of fasting glucose and lipids, to include LDL, HDL, triglycerides, and total cholesterol. Laboratory results

will be sent to the PCP per the laboratory and practice's standard operating procedures. The practice will in turn provide the results to KUMC study personnel (see section E1 for specifics).

**Questionnaires.** Self-report questionnaires will be administered via on-line REDCap surveys sent by email or by hard copy surveys sent via regular mail, depending on patient preference. Patients will be asked to complete questionnaires at all five time points (baseline, 6, 12, 18, and 24 month visits). Patients must complete the baseline questionnaires prior to enrolling in the trial (see section C1).

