**Fruit and Vegetable Screener** is a brief 2 item questionnaire assessing the number of cups of fruits and vegetables eaten each day.

**AUDIT C (Alcohol consumption):** The Alcohol Use Disorders Identification Test- Consumption (AUDIT-C) is a well-established 3-item screener of typical alcohol consumption and identifies individuals with a pattern of hazardous alcohol use. An additional item assesses heavy drinking as the largest number of drinks consumed during a single drinking episode in the past 6 months.

**Program Satisfaction and Experience of Care.** Satisfaction with program components and experiences of care will be assessed from surveys developed for this trial, in addition to process interviews described below.

Table 5. Measures						
	MONTH					EST. TIME
In-Clinic Measures**						
	0	6	12	18	24	
Weight	X	X	*	X	X	1 minute
Height	X					1 minute
Blood draw	X	X			X	5-10 minutes
Blood pressure	X	X		X	X	5 minutes
Questionnaires (phone, on-line or mail surveys)						
Demographic info and updates	X		X		X	5 minutes
Medical history, smoking and weight loss history 42,82/ updates	X	X	X	X	X	5-10 minutes
Medication information and updates	X	X	X	X	X	2-5 minutes
SF-12 (general quality of life)	X	X			X	2-5 minutes
Impact of Weight on Quality of Life –Lite (IWQOL-L)	X	X			X	5minutes
Pittsburgh Sleep Quality Index (PSQI)	X	X			X	2-5 minutes
Perceived Stress Scale (PSS)	X	X		X	X	1-2 minutes
Patient Health Questionnaire-9 (PHQ-9)	X					1-2 minutes
Patient Reported Outcomes Measurement Information System-29 (PROMIS-29)	X	X		X	X	2-3 minutes
Modifiable Activity Questionnaire (MAQ)	X	X	X	***	X	2-5 minutes
NCI’s Energy Screener  fruit and vegetable screener, Frequency of Fast Food and Sugar Sweetened Beverage Consumption  , and alcohol consumption 	X	X	X		X	5 minutes
Program Satisfaction and Experience of Care		X			X	2-5minutes

\*12-month weight is self-report, no in-person visit.

\*\*An in-home visit or a visit at another location convenient for the patient may be conducted, if a patient is unable to come to the clinic for the visit.

\*\*\*MAQ added at 18-months after initiating 18-month visits, based on patient feedback that measures were too focused on mood-related outcomes only; 18-month MAQ measure will not be included in the primary analysis of PA outcomes.

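### The 5% and 10% responder analysis leaves out the 18-month and continuous weights, so 24-month responder rates will be somewhat too high if people who regain weight are lost preferentially

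*Combined protocol and SAP*

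**What the plan says.** Section II.C1 (Primary aims 1-3) sets out three analyses of weight.

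- Weight change: "We will fit a hierarchical linear mixed model with longitudinal weight change at 6, 18, and 24 months study visits".
- Percent loss: "In secondary analysis, percent weight loss will also be compared across the three groups using the same approach".
- Responders: "Clinical cutpoints of 5% and 10% will be compared across arms at 6 and 24 months using generalized linear mixed models".

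The third departs from the first two. The outcome becomes binary and the 18-month visit drops out. The text does not say whether the 6- and 24-month results are modelled jointly or separately, or how a participant without a 24-month weight is classified.

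The only missing-data rule is in the Missing data paragraph of II.C1: "In the absence of differential loss to follow-up, missing weight data will be treated as missing at random and addressed using maximum likelihood methods". It contains nothing specific to the cutpoints. On expected loss the same paragraph says "we expect to retain a minimum of 80% of participants (with a goal of 90%) at 24 months across all three treatment arms".

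On what is collected, II.E2e says "Weight, and blood pressure will be directly measured and recorded at baseline, 6, 18, and 24 months during in-clinic assessment visits". II.E2e and III.C4 also allow chart review to recover missing weights.

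**The concern.** Maximum likelihood corrects for missing data only through the variables in the likelihood. In the cutpoint model, someone missing at month 24 contributes at most a yes/no from month 6. If each visit is fitted separately, that person contributes nothing to the 24-month comparison. Section II.E2d places the maintenance phase after month 6, so regain after month 6 is what a 6-month indicator cannot show. The 18-month weight shows much of it, and the primary model already uses that weight.

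If regain makes loss more likely, missing at random may be reasonable for the continuous model and fail for the binary one, in the same participants. The share losing 5% or 10% at 24 months is a figure that patients and practices are likely to read, and it would be on the high side.

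**Working it through.** **1. The plan's own figure.** The documents give no rate, power or sample size for the responder analysis. The nearest figure is the 80% power in II.C3 for continuous weight (2.75 kg, SD 8, ICC 0.05, 40 per clinic, 480 per arm, alpha 0.025; two-sided is assumed, since sidedness is not stated).

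- Design effect = 1 + 39 × 0.05 = 2.95; effective n = 480 / 2.95 = 162.7 per arm.
- SE = 8 × √(2 / 162.7) = 0.887 kg; 2.75 / 0.887 = 3.10.
- Power = Φ(3.10 − 2.24) = about 80.5%. The figure reproduces.

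**2. What each analysis estimates at 24 months.** Let Y6 and Y24 be responder status.

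- Separate visits (complete case): P(Y24 = 1 | seen at 24 months).
- Joint 6 + 24 binary: Σ P(Y24 = 1 | Y6 = k, seen) × P(Y6 = k), over k = 0, 1. With two visits, a model with visit means and a patient intercept is saturated, so it reduces to this sum. It is unbiased only if, within arm, loss at 24 months depends on nothing beyond Y6.
- Continuous: predict 24-month weight from the 6- and 18-month weights, then apply the cutpoint.

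**3. Assumed inputs (none is in the documents).** Mean percent loss at 6/18/24 months: FFS 3/2/1, DM 7/5/3.75. SD 6/7.5/8. Correlations 0.75 (6-18), 0.65 (6-24), 0.90 (18-24). Logistic loss at 24 months; everyone has 6- and 18-month weights. There are 600,000 simulated participants per arm. The 20% and 10% loss levels are the plan's retention floor and goal.

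**4. Responder rates at 24 months (FFS / DM, %).**

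| Cutpoint and loss scenario | True | Complete case | Joint 6 + 24 | Continuous |
|---|---|---|---|---|
| 5%; 20% lost, odds ×2 per SD of poorer 18-month result | 30.8 / 43.7 | 34.6 / 48.1 | 33.1 / 46.5 | 30.8 / 43.8 |
| 5%; 10% lost, odds ×2 | 30.8 / 43.9 | 32.6 / 46.1 | 31.9 / 45.2 | 30.8 / 43.9 |
| 5%; 20% lost, odds ×3 | 31.0 / 43.7 | 36.1 / 50.0 | 34.1 / 47.6 | 31.0 / 43.7 |
| 5%; 20% lost, odds ×2 per SD of 6-to-18-month regain | 30.9 / 43.9 | 33.3 / 46.7 | 33.5 / 46.9 | 30.9 / 43.9 |
| 5%; 20% lost, unrelated to weight | 30.8 / 43.7 | 30.8 / 43.8 | 30.8 / 43.8 | 30.8 / 43.7 |
| 10%; 20% lost, odds ×2 | 13.1 / 21.7 | 15.1 / 24.6 | 14.4 / 23.4 | 13.0 / 21.7 |

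In the first row the joint excess is 33.1 − 30.8 = 2.3 and 46.5 − 43.7 = 2.8 points. The complete-case excess is 3.8 and 4.4. At 10% loss the excesses are 1.1 and 1.3 (joint) and 1.8 and 2.2 (complete case). When loss follows regain between 6 and 18 months, the 6-month indicator gives no help.

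**5. Arm difference, 5% cutpoint.**

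- Equal 20% loss, odds ×2: true 12.9, joint 13.4, complete case 13.6, a shift of 0.5 to 0.7 points. The largest shift in any similar-loss run, at either cutpoint, is 1.4 points.
- FFS 15% and DM 25% lost, odds ×1.6 to ×3.3, true difference about 13: joint 14.4 to 15.9, complete case 15.1 to 17.4.
- The reverse split: joint about 12, complete case about 11 to 12.
- Continuous imputation stays within about 0.1 point of the truth in these unequal-loss runs.

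**6. Scale.** If the ICC of 0.05 also held for responder status and all 480 per arm were observed, the SE of the difference would be √[2.95 × (0.308 × 0.692 + 0.437 × 0.563) / 480] = 0.053, or 5.3 points.

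**7. Limits of the remedy (20% loss, odds ×2).** If half of those lost also lack the 18-month weight, or if loss depends on the unseen 24-month weight, continuous imputation is still about 0.7 to 0.9 points too high.

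**The case against.** The strongest case against is that the planned analysis compares arms, and the comparison hardly moves. With similar loss the shift is a small fraction of a standard error. That stands.

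A reader might infer that responder rates will be too high in every arm. The documents do not support that without a condition. Nothing in them says that people who regain are lost preferentially, and if loss is unrelated to weight there is no excess. Chart review (II.E2e, III.C4), the four-month window for the 24-month visit and off-site visits (II.E2e) all work to recover the people concerned.

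A reader might also infer that the arm comparison would be materially wrong. That needs unequal loss. The 15% versus 25% split is an assumption, and 25% exceeds the loss that the plan expects in any arm. The plan applies its missing-at-random rule only when loss is not differential. That it names no method for the other case is a separate gap.

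Two further points stand. The near-exact recovery by continuous imputation follows from the simulation's design, in which loss depends on an 18-month weight that everyone has. And the data structure of the generalized linear mixed model is not specified, so the limit to 6-month status is read from the named visits and the binary outcome.

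None of this removes the point. Even the more generous joint reading leaves out the 18-month weight. II.C1 lets the analysis plans be adapted, which permits a better method but does not commit to one.

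**Conclusion.** The point holds as a conditional weakness in a secondary analysis. As written, the cutpoint comparison cannot use the 18-month or continuous weights for participants missing at 24 months. If people who regain are lost preferentially, the 24-month 5% responder rates are too high: about 2 to 3 points (joint) or 4 points (complete case) at 20% loss, and about 1 to 2 points at 10%. The excess is about zero if loss is unrelated to weight. The effect on the arm difference is under about 1.5 points with similar loss. With a 15% versus 25% split it is about 1 to 3 points (joint) or 1 to 4 points (complete case).

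These sizes rest on assumed means, SDs, correlations and loss mechanism, because the documents supply none for this endpoint. The primary weight model and the percent-loss analysis already use all three follow-up visits and are not affected. The argument concerns the 24-month rates; the 6-month rates gain little from it.

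**What to change.** Specify in II.C1 that the cutpoints are derived after imputation:

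1. Multiply impute missing continuous weight separately by arm, with clinic as a random effect, using baseline, 6-, 18- and 24-month weights and including values recovered by chart review.
2. Derive the 5% and 10% indicators in each completed data set.
3. Fit the planned generalized linear mixed model in each, stating whether visits are joint or separate, and pool by Rubin's rules.
4. Add a delta-adjusted sensitivity analysis, in which imputed weights are shifted towards regain, to cover loss that depends on the unseen 24-month weight.

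Counting missing participants as non-responders is not a substitute. In the 20% loss, odds ×2 scenario it gives 27.7% and 38.5% against true rates of 30.8% and 43.7%, so it errs low.

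The cost is some programming and reliance on an imputation model that is roughly normal for weight. No new data are needed. The change cannot remove all bias: about 0.7 to 0.9 points remain in the scenarios of step 7 of the working.

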### **Secondary aim 4: patient-centered outcomes**

Each patient-centered outcome at 24 months (and all relevant intermediate study visits) will be compared across all treatment arms using separate hierarchical linear mixed models.

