##### *Hypotheses:*

1. **PCMH** is more effective than **FFS** in reducing weight at 24 months.
2. **DM** is more effective than **FFS** in reducing weight at 24 months.
3. **DM** is more effective than **PCMH** in reducing weight at 24 months.
- 4a. **PCMH** is more effective than **FFS** at improving patient-centered outcomes, including blood pressure, laboratory measures (fasting glucose and lipids), quality of life, sleep, and stress.
- 4b. **DM** is more effective than **FFS** at improving patient-centered outcomes, including blood pressure, laboratory measures (fasting glucose and lipids), quality of life, sleep, and stress.
5. **DM** and **PCMH** will show larger effects over **FFS** for those with lower education, lower income, who travel longer distances to receive care, and who are employed full-time.
6. Aim 6 includes exploratory qualitative and quantitative process measures with no explicit hypotheses.

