### **Secondary aim 6: evaluate the reach and sustainability of the interventions with the RE-AIM framework (Reach, Adoption, Implementation, Maintenance)**

Adoption within KUMC-affiliated sites will be evaluated by comparing practice characteristics across participating and non-participating practices (that were contacted about the study) using two sample comparisons (chi square or t-tests). After aggregating to the practice level, patient-level factors for reach (e.g., participation rates) and implementation (e.g., session attendance, ratings of care) will be tested and compared across arms using separate analysis of variance (ANOVA) models. Maintenance of weight loss services at the practice-level will be reported as simple frequencies.

**Potential confounders:** For all statistical models, sensitivity analyses will be performed using the models above but also adjusting for potential confounders among the baseline variables identified as varying across arms based on their standardized differences.

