## **E. Specific Methods and Techniques Used Throughout the Study (Figure 4. Study Flow; page 26)**

### **E1. Laboratory tests**

Blood draws will occur at baseline, 6 months, and 24 months. Blood draws will be collected at the local practices by a phlebotomist or nurse. The practice staff will monitor and record self-reported fasting compliance. The collection, processing, analysis and storage of samples will differ depending on the site.

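### The Aim 4 model states no baseline term, although every named outcome is measured at baseline; prespecified adjustment would recover precision at no data cost

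*Combined protocol and SAP*

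**What the plan says.** Section II.C1, under Secondary aim 4, gives the model in one sentence: "Each patient-centered outcome at 24 months (and all relevant intermediate study visits) will be compared across all treatment arms", by separate hierarchical linear mixed models. It mentions no baseline covariate, no change score and no baseline visit in the response.

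The weight analysis, just before it in II.C1, does define its response: "We will fit a hierarchical linear mixed model with longitudinal weight change at 6, 18, and 24 months study visits".

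Hypotheses 4a and 4b (Section I.A2) say that PCMH and DM, respectively, are more effective than FFS "at improving patient-centered outcomes, including blood pressure, laboratory measures (fasting glucose and lipids), quality of life, sleep, and stress". That wording implies change but does not define what is modelled.

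Baseline values exist for every outcome named. Section II.E2e says "Weight, and blood pressure will be directly measured and recorded at baseline, 6, 18, and 24 months". Section II.E1 schedules blood draws at baseline, 6 and 24 months. Table 5 marks month 0 for SF-12, IWQOL-L, PSQI and PSS, and the baseline questionnaires must be completed before enrolment.

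The paragraph on potential confounders, which closes II.C1 and covers all the statistical models, says "sensitivity analyses will be performed using the models above but also adjusting for potential confounders among the baseline variables identified as varying across arms", judged by standardized differences.

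**The concern.** A patient's baseline blood pressure, lipids or quality-of-life score usually predicts the 24-month value of the same measure. A model without it leaves stable differences between patients and between practices in the error term. With only 12 practices per arm, intervals are then wider than the collected data require, and a real difference is more easily missed.

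The sensitivity analysis does not repair this. A prognostic baseline value reduces variance whether or not the arms look different on it. An adjustment made only when imbalance is seen, and only outside the main analysis, cannot secure that gain.

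The silence also leaves a choice open. Follow-up value, change score and adjusted model all fit the Aim 4 sentence and can give different answers, so the choice could be made after the data are seen.

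**Working it through.** **Inputs from the documents (II.C3).** 12 practices and 480 participants per arm, 40 per practice, ICC 0.05. For the primary weight contrast only: difference 2.75 kg, SD 8, type I error 0.025 per comparison, power 80%.

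**Assumptions.** The documents give no power, alpha, ICC or baseline-to-follow-up correlation for Aim 4. I borrow the ICC of 0.05, take alpha as two-sided 0.05, use the same ρ within and between practices, and show a range for ρ.

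**1. The plan's own figure.**
- Design effect: 1 + 39 × 0.05 = 2.95. Effective n per arm: 480/2.95 = 162.7.
- SE of the weight contrast: 8 × √(2/162.7) = 0.887 kg.
- Power, normal approximation, two-sided 0.025: Φ(2.75/0.887 − 2.241) = 80.5%.

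This agrees with the stated 80%, so the same set-up is used below.

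**2. Follow-up values only, in SD units.**
- SE = √(2 × 2.95/480) = 0.111 SD.
- Effect detectable with 80% power: (1.960 + 0.842) × 0.111 = 0.311 SD.

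**3. Variance of the contrast relative to follow-up values only.**
- Baseline as covariate: 1 − ρ².
- Change score: 2(1 − ρ).
- Change score minus covariate: 2(1 − ρ) − (1 − ρ²) = (1 − ρ)², which is never negative. Adjustment is therefore at least as precise as either alternative.

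**4. Power at the fixed effect of 0.311 SD.** Power = Φ(2.802/√V − 1.960), with V from step 3.

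| ρ | V adjusted | Follow-up only | Adjusted | Change score |
|---|---|---|---|---|
| 0.3 | 0.91 | 80% | 83.6% | 65.8% |
| 0.5 | 0.75 | 80% | 89.9% | 80.0% |
| 0.7 | 0.51 | 80% | 97.5% | 95.1% |

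The gain over follow-up values is about 4, 10 and 17 points. With a t distribution on 33 degrees of freedom, and the effect reset to 80% unadjusted power, the adjusted figures are the same to the first decimal place.

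**5. The same result as variance and detectable difference.** Leaving out baseline multiplies the variance by 1/(1 − ρ²): 1.10, 1.33 and 1.96. With adjustment, the detectable difference falls from 0.311 SD to 0.296, 0.269 and 0.222 SD.

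**6. If change scores are intended.** At ρ = 0.7 the gap in the table is 2.4 points, partly because both figures are near the ceiling. Resetting the effect so that the change score has 80% power gives adjusted power Φ(2.802 × √[2(1 − ρ)/(1 − ρ²)] − 1.960). This is 89.9% at ρ = 0.5, 86.0% at 0.7 and 84.0% at 0.8: gains of about 10, 6 and 4 points.

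**7. Retention at the 80% minimum (II.C1).** With 32 analysed per practice the design effect is 1 + 31 × 0.05 = 2.55, and the detectable difference on follow-up values rises to 0.323 SD. The variance ratios in step 3 do not change.

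**8. Chance baseline difference between two arms.** Its SE is also 0.111 SD, so its 95% range is about ±0.22 SD. A share of about ρ carries into an unadjusted 24-month contrast. This is already part of the standard error in step 2 and is not added to it.

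**The case against.** The strongest reply is that the Aim 4 sentence neither says that raw levels are analysed nor rules out a baseline term. The hypotheses speak of improvement and the adjacent weight model uses change, so change could be intended here too. That stands: a comparison of follow-up values is the natural reading, not a stated fact. What is firm is that the response and the handling of baseline are not stated. The remedy is the same either way, because adjustment is at least as precise as both alternatives, but the larger gains in step 4 belong to the follow-up-only reading.

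A reader might infer that baseline differences bias the arm contrasts. The documents do not support that as a second harm. Practices are randomized, so a chance difference is sampling error already in the interval, and it does not raise the type I error. Consent forms that vary by arm and a longer FFS enrolment period make arm-related selection conceivable, but the plan says nothing of its size or direction, and this point does not depend on it. The sensitivity analysis could also bring in an outcome's baseline value where imbalance is seen, so imbalance would not go wholly unexamined.

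A reader might also infer from "The collection, processing, analysis and storage of samples will differ depending on the site" that laboratory offsets by practice make the loss much larger for glucose and lipids. Section II.E1 supports practice-specific laboratories only for the KUMC and UNMC practices. The ten Marshfield practices share one laboratory, and randomization is stratified by institution. No document gives the size or stability of any offset, so a higher practice-level correlation, and the larger gain it would imply, would be conjecture.

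Finally, Aim 4 is secondary and has no stated power target. That limits the stakes but does not remove the inefficiency.

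**Conclusion.** The point holds as a missing specification with a calculable cost. If follow-up values alone are analysed, Aim 4 gives up about 4 points of power at ρ = 0.3, 10 at 0.5 and 17 at 0.7, for an effect with 80% power unadjusted. If change scores are analysed, the loss is about 10 points at ρ = 0.5 and smaller at higher ρ. These figures rest on the assumed ρ, on equal ρ within and between practices, on an ICC borrowed from the weight calculation, and on an assumed two-sided alpha of 0.05. The direction does not depend on the value of ρ: any ρ above zero favours adjustment over follow-up values, and any ρ below one favours it over change.

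Chance imbalance between arms is this same loss of precision seen another way, not a separate bias. The primary weight analysis and its stated 80% power are untouched. The change should be made, but the trial's main conclusion does not depend on it.

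**What to change.** In Section II.C1, Secondary aim 4, state that the main model for each outcome includes that outcome's own baseline value as a prespecified covariate, whether or not imbalance is observed. An equivalent is to place baseline in the response vector with a common mean across arms. State the response scale in the same sentence. The standardized-difference adjustment can remain as a sensitivity analysis.

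A practice-mean baseline term for glucose and lipids is optional. So are baseline slopes that differ by visit and extension to the physical-activity and diet scores.

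The cost is one sentence. No new data are needed, because all the baseline values are already scheduled for collection.
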